A Patient-Centered Strategy for Improving Diabetes Prevention in Urban American Indians

02266576

Statistical Analysis Plan

October 9, 2019

CHANGES FROM ORIGINAL PROTOCOL

1. The second investigational site was changed from Indian Health Center of Santa Clara Valley to the Timpany Center at the San Jose State University Research Foundation.
2. Blood samples were obtained by fingerstick method rather blood draw.

METHODS

The primary model for participant j at time k nested in cohort i

$$\begin{aligned} \text{Outcome}_{ijk} = & \beta_0 + \beta_{0i} \\ & + \beta_{0ij} + \beta_1 \text{Intervention}_j + \beta_2 \text{Month6}_{jk} + \beta_3 \text{Month12}_{jk} + \beta_4 \text{Month18}_{jk} \\ & + \beta_5 \text{Intervention}_j * \text{Month6}_{jk} + \beta_6 \text{Intervention}_j \\ & * \text{Month12}_{jk} + \beta_7 \text{Intervention}_j * \text{Month18}_{jk} + \beta_8 \text{Gender}_j + \varepsilon_{ijk} \end{aligned}$$

will be used to test the co-primary hypotheses that BMI will decrease and quality of life will increase in the enhanced DPP arm relative to the standard DPP arm upon completion of the study. The linear regression model includes a random intercept β_{0i} to account for within cohort correlation, a random intercept β_{0ij} to account for within participant correlation, and adjusts for gender (Gender_j), the stratification factor for randomization. Intervention_j indicates that participant j is in the enhanced DPP arm and Month6_{jk} , Month12_{jk} , and Month18_{jk} indicate whether observation k from subject j is at month 6, 12, or 18, respectively. To test whether the change in the primary outcome from baseline at 12 months differs between the standard and enhanced arms, we will test the null hypothesis that $\beta_6 = 0$ using the Wald test. Each outcome will be tested at a two-sided $\alpha = 0.05$ for an overall $\alpha = 0.10$.

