The primary analyses will follow the intent-to-treat principle and will use all available data. We will describe any missing data and will conduct sensitivity analyses to evaluate the impact of the missing data on our conclusions. Sensitivity analyses considered to evaluate the robustness of our findings to the presence of missing data will include multiple imputation methods and worst-case imputation where missing values are filled with an extreme value (eg 5% greater than value observed at baseline), which can be used to determine how extreme the unobserved missing values would need to be in order to change the conclusion of the trial.^{51,52} Secondary analyses will replace the primary outcome in the model above with secondary outcomes.

Additional secondary analyses will consider pre-specified moderators and mediators (depressive symptoms, coping skills, and social support/community cohesion) of the primary outcomes. We will investigate the moderators and mediators using mixed effects linear regression by including an interaction term of treatment and the hypothesized moderator and centering the independent variables.^{53,54}

SAMPLE SIZE AND DATA INTERPRETATION

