Our study was designed to provide sufficient statistical power to test the study's co-primary hypothesis that the enhanced DPP will result in greater weight loss and quality of life improvement compared to the standard DPP. In determining the sample size we considered the definition of clinically significant weight loss, the standard deviation of weight change in past clinical trials of lifestyle interventions, and acceptable levels of Type I and Type II errors. Our power estimates are based on simplified assumptions and the actual power may be different because of the correlated errors induced by the cohort effect and the repeated measures over time. In the original DPP trial, the average weight loss in the intensive intervention arm was $6.9\% \pm 4.5\%$ after 6 months of follow up and $4.9\% \pm 7.4\%$ at the end of the trial (mean follow-up of 3.2 years).⁵⁵ This percent weight loss is similar to other studies and greater than that observed in the SDPI evaluation where Jiang et al reported a percent weight loss of 4.4% following the 16-week program.¹⁰ Based on this literature, we expect a mean percent weight loss of 4.0% in the standard DPP and 6.5% in the enhanced DPP. To be conservative, we powered the study to be able to detect a difference of 2.0%. Dividing a 2.0% difference (6.0%-4.0%) by the DPP SD (4.5%) yields an effect size of approximately 0.45. A sample of 81 participants per arm will be required to compare the standard and enhanced arms for an effect size of 0.45 at a two-sided $\alpha=0.05$ with 80% power. We estimate 20% will be missing BMI at follow-up and have therefore inflated the initial sample size to 102 participants per arm. As the secondary analyses are exploratory, no adjustment for multiple testing will be made for secondary analyses. The secondary analyses are not intended to produce clinically actionable results, but rather to supplement conclusions based on the primary analysis and to inform future research. They will be interpreted properly within that context, considering the totality of evidence available.

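### The SAP's only worst-case fill, 5% above baseline, is a gain for quality of life, and for BMI its effect on the arm difference depends on which arm has more missing data

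*SAP*

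**What the plan says.** The SAP's Methods section names two co-primary hypotheses, that "BMI will decrease and quality of life will increase in the enhanced DPP arm relative to the standard DPP arm". The benefit is therefore a fall in one outcome and a rise in the other. The tested quantity is a between-arm contrast: "To test whether the change in the primary outcome from baseline at 12 months differs between the standard and enhanced arms", the SAP tests the arm-by-month-12 interaction coefficient, β6.

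The primary analysis is intention-to-treat on all available data. The missing-data sensitivity analyses "will include multiple imputation methods and worst-case imputation". The second of these is described as "worst-case imputation where missing values are filled with an extreme value (eg 5% greater than value observed at baseline", and the SAP adds a purpose: "which can be used to determine how extreme the unobserved missing values would need to be in order to change the conclusion of the trial".

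The SAP does not give a fill value or direction for quality of life, does not say whether the fill may differ between arms, and gives no range of values to step through. Multiple imputation is named without detail. The Sample Size section expects 20% of participants to be missing BMI at follow-up and does not split that figure by arm.

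**The concern.** A worst-case analysis should push the tested result in the harmful direction. The example raises two doubts.

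- **Outcome direction.** One upward fill cannot be adverse for both an outcome that should fall and an outcome that should rise. For quality of life, a participant with missing data would be credited with an improvement over baseline.
- **Arm contrast.** β6 compares arms. Giving the same poor BMI value to everyone with missing data penalises each arm in proportion to its own missingness. If standard DPP has more missing data, the fill favours DPP+.

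At stake is how far the robustness statement can be trusted. With a fifth of follow-up BMI expected to be missing, readers will rely on this analysis to judge whether a positive finding survives.

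**Working it through.** **Inputs from the documents.** From the SAP's Sample Size section: "we expect a mean percent weight loss of 4.0% in the standard DPP and 6.5% in the enhanced DPP"; "Dividing a 2.0% difference (6.0%-4.0%) by the DPP SD (4.5%) yields an effect size of approximately 0.45"; two-sided 5% test with 80% power; 81 evaluable and 102 randomised per arm; 20% missing overall. The Protocol (section 2a) also gives 102 per arm.

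**Inputs assumed.** Missingness by arm is varied around 20%. Percent weight change stands in for percent BMI change, which is exact if height is constant. The SD of percent change in quality of life is taken as 10% to 20%, because neither the instrument nor its SD is given. That a higher score is better is inferred from the hypothesis.

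**The plan's own figure.** 2.0/4.5 = 0.444. A two-sample t-test at two-sided 5% with 80% power needs 80.44, so 81 per arm. Then 81/0.8 = 101.25, so 102. Both figures reproduce.

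**Method.** Let m be an arm's missing fraction, μ its mean percent change among those observed, and f the fill.
- Arm mean = (1 − m)μ + m·f.
- Arm variance = (1 − m)SD² + m(1 − m)(μ − f)².
- D = DPP+ mean minus DPP mean; for BMI, negative favours DPP+.
- SE = √[(sum of the two arm variances)/102], and z = D/SE.

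This approximates the mixed model rather than reproducing it.

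**BMI, no true effect (both arms −4%, SD 4.5, f = +5% in both arms).** The gap between fill and observed mean is 5 − (−4) = 9 points, so D = 9 × (DPP+ missing fraction − DPP missing fraction).

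| Missing, DPP/DPP+ | DPP mean | DPP+ mean | D | Chance of a false finding for DPP+ (nominal 2.5%) |
|---|---|---|---|---|
| 20%/20% | −2.2 | −2.2 | 0 | 2.5% |
| 25%/15% | 0.75(−4) + 0.25(5) = −1.75 | 0.85(−4) + 0.15(5) = −2.65 | −0.9 | 22% |
| 30%/10% | 0.7(−4) + 0.3(5) = −1.3 | 0.9(−4) + 0.1(5) = −3.1 | −1.8 | 67% |

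Simulation with 20,000 runs gave 2.6%, 22% and 67%. The 1.8 points is 1.8/2.0 = 90% of the difference the trial is powered to detect. Reversing the imbalance reverses the sign: 15%/25% gives +0.9, against DPP+.

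**BMI, observed difference of −2.0 (−4% v −6%), same fill in both arms.** Without the fill, z is about −2.8 in each row.

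| Missing, DPP/DPP+ | DPP mean | DPP+ mean | D | z |
|---|---|---|---|---|
| 20%/20% | −2.2 | −3.8 | −1.6 | −2.01 |
| 25%/15% | −1.75 | −4.35 | −2.6 | −3.31 |
| 15%/25% | −2.65 | −3.25 | −0.6 | −0.75 |

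**An arm-specific adverse fill for comparison.** At 20%/20%, give missing DPP+ participants +5% and missing DPP participants their own arm mean. DPP stays at −4.0 and DPP+ becomes 0.8(−6) + 0.2(5) = −3.8, so D = +0.2 (z = 0.28). The common fill leaves the benefit nominally significant; this one removes it.

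**Quality of life, no true effect, mean change 0 among those observed, missing 10% in DPP and 30% in DPP+.** With +5% in both arms, DPP = 0.1 × 5 = 0.5 and DPP+ = 0.3 × 5 = 1.5, so D = +1.0 in favour of DPP+. The error rate in that direction is 11.9%, 7.6% or 5.9% for an SD of 10%, 15% or 20%. With −5% in both arms, D = −1.0.

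The sign depends on the observed change. If both arms gain 10% among those observed, DPP = 0.9(10) + 0.1(5) = 9.5 and DPP+ = 0.7(10) + 0.3(5) = 8.5, so D = −1.0, against DPP+. The switch comes at an observed gain of 5%.

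**The case against.** The best defence is that the sentence is governed by its label and purpose rather than by its example. The 5% is marked as an example, a gain cannot be a worst case for quality of life, and the stated aim of finding how extreme missing values must be already describes a tipping-point analysis. On that view only specification is missing. Four parts of this defence stand.

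- A reader might infer that the SAP prescribes a favourable fill for quality of life, or that this outcome cannot be stress-tested at all. Neither follows. The example does not rule out another value or direction, and multiple imputation is planned as well. Even +5% works against DPP+ when DPP+ has more missing data and observed gains exceed 5%.
- A reader might take it as stated that both arms receive the same fill. The SAP is silent on arm. It is the natural reading, and the BMI figures for a common fill depend on it.
- A reader might infer that the BMI fill always helps DPP+. It does not. At the only planning figure, 20% with no split by arm, it creates no bias under the null and weakens a 2.0-point difference. With more missing data in DPP+ it is a severe test. Nothing in the documents predicts that standard DPP will lose more people, and the 1.8-point case needs a threefold imbalance.
- Calling the created difference false assumes that those with missing data changed as those observed did, which is the assumption under test. If they truly regained weight, part of the difference would be real.

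What does not stand is that this is only missing detail. Varying the size of a common upward fill corrects neither the direction for quality of life nor the symmetry between arms.

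**Conclusion.** The concern holds in a limited form. The only fill the SAP illustrates is not a worst case for quality of life, given that higher is better. For BMI, applied alike in both arms, it is not reliably adverse to the arm difference: it can create, enlarge or shrink a benefit depending on where data are missing. The sizes are those tabulated above. They rest on the SAP's 4% and 6% losses and SD of 4.5, on assumed splits around 20% missing, and on a simple two-sample approximation.

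A reader might go further and conclude that the trial's result is biased, or that any finding of robustness would be wrong. The documents do not support that. The primary all-available-data result is untouched, and this is one of at least two sensitivity analyses. The risk is false reassurance: a positive result could be called robust after a check that did not push against it. It should be corrected before the analysis is run.

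**What to change.** Keep the tipping-point purpose and replace the example with a defined procedure.

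1. State the adverse direction for each co-primary: BMI up, quality of life down.
2. Build on the multiple imputation already planned. If the primary result favours DPP+, impute DPP under missing-at-random and shift the imputed DPP+ values in the harmful direction by a growing delta.
3. If the primary result does not favour DPP+, vary the shift in each arm, so that a null or opposite finding is also tested, in keeping with the two-sided tests.
4. Report, for each co-primary, the delta at which the conclusion changes, together with the amount of missing data in each arm.

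The cost is a sentence or two in the SAP and a short loop around the imputation. No new data are needed. The sensitivity result may look less favourable than under a common fill.

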Participants will be recruited by Timpany Center staff and community members. If they are otherwise eligible except that some of their information is more than 3 months old, we will conduct a clinical screening to collect recent blood pressure, and blood test for cholesterol and blood sugar. They will consent in- person for the clinical screening. Eligible participants will receive an explanation about the study and sign the full study consent form. After signing the consent form, the participant completes baseline data collection. This includes an interviewer administered questionnaire, a blood test, clinical measurements, and wearing a pedometer for 7 days. After all baseline data is collected, the participant is randomly assigned to ONE of two groups: 1) diabetes prevention program (DPP) or 2) enhanced diabetes prevention program (DPP+).

There are 102 people in the standard DPP and 102 people in the enhanced diabetes prevention program to address historical trauma (DPP+). Participants will complete 3 evaluations during the research study: baseline, 5 months (1 week following the conclusion of intervention). Participants enrolled in the last cohorts will not have as many follow-up evaluations as those enrolled in initial cohorts. The evaluations include blood draws, other measurements (blood pressure, height, weight, and waist circumference), and a series of questionnaires. Blood samples and other measurements will be collected at all of the evaluation visits (baseline, 5 months, 8 months, 14 months, and 20 months) after a more than 8 hour fast. The volume of most blood samples will be 20 cc's (approximately 1.5 tablespoons). Any samples left over after analysis will be destroyed when the study is completed. Questionnaires include a series of questions about their eating patterns, physical activity habits, smoking status, past medical history, current medications, use of additional health care resources, resilience, and emotional status. Questionnaires will be filled out at the clinic visits at baseline, 5 months, 8 months, 14 months, and 20 months.

b. Procedure Risks

We have designed this study to be least risky through the following means:

- 1) The intervention targets improvement of behaviors (diet, exercise, stress reduction) that can help decrease weight; thereby, decreasing the chance of cardiovascular disease.
- 2) The intervention recommendations are based on accepted clinical guidelines.

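### The one method stated for both moderators and mediators, a treatment-by-moderator interaction, cannot on its own support or refute mediation

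*SAP*

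**What the plan says.** In METHODS, after the missing-data text, the SAP plans additional secondary analyses of "pre-specified moderators and mediators (depressive symptoms, coping skills, and social support/community cohesion) of the primary outcomes". The three constructs stand in one list, and none is assigned to one role or the other. The next sentence takes moderators and mediators together as its object and gives one method, mixed effects linear regression, carried out "by including an interaction term of treatment and the hypothesized moderator and centering the independent variables". References 53 and 54 are cited at that sentence.

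Other places bear on this:

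- The primary model (SAP, METHODS) has arm, visit and arm-by-visit terms. Its test of β6 is introduced with the words "To test whether the change in the primary outcome from baseline at 12 months differs".
- On secondary outcomes the SAP says: "Secondary analyses will replace the primary outcome in the model above with secondary outcomes". Neither document lists those outcomes.
- Protocol section 2a repeats the questionnaires: "Questionnaires will be filled out at the clinic visits at baseline, 5 months, 8 months, 14 months, and 20 months". No visit is named for the moderator or mediator value.
- SAP, SAMPLE SIZE AND DATA INTERPRETATION, calls the secondary analyses exploratory and adds: "The secondary analyses are not intended to produce clinically actionable results".

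**The concern.** Moderation asks whether the treatment effect differs between people with high and low values of a variable. Mediation asks whether treatment changes the variable and that change then affects the outcome. Either can be present without the other, and the only term the SAP names addresses the first question.

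The enhanced programme adds psychosocial support, so later work will want to know whether any benefit runs through depressive symptoms, coping or social support. A null interaction read as absence of mediation, or a significant one read as a mechanism, would mislead that work.

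**Working it through.** **1. Structure.** Let T be treatment (0/1), M the psychosocial variable and Y the outcome:

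- M = a·T + error
- Y = c′·T + b·M + g·T·M + error

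The stated interaction term estimates g. With g = 0 the indirect effect is a·b, so under full mediation (c′ = 0, a and b non-zero) the stated term is zero however large a·b is. With a = 0 and g non-zero, the indirect effect is a·(b + g) = 0 in the treated arm and a·b = 0 in the control arm, yet the stated term is non-zero. This does not depend on any numerical value.

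**2. Inputs for an illustration.** The SAP supplies only the 81 per arm. It reproduces: 2.0/4.5 = 0.444; a two-sample t-test at two-sided 0.05 and 80% power needs 80.44, so 81; and 81/(1 − 0.20) = 101.25, so 102. Everything else is assumed: four visits, person SD 1.0, residual SD 0.7, SD of M about 1, M measured at every visit, cohort effect omitted. The fitted model is the SAP's primary model plus centred M and T × M. The simulations used 1000 to 2000 runs; ranges below are across repeated runs.

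| Assumed situation | Stated T × M term rejects |
|---|---|
| Full mediation, a = b = 0.5 or a = b = 0.3, g = 0 | about 4 to 6% |
| No mediation (a = 0), g = 0.1 per SD of M | 22 to 24% |
| No mediation (a = 0), g = 0.2 | 66 to 69% |
| No mediation (a = 0), g = 0.3 | 94 to 95% |

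The first row is the null rate by construction, since g = 0.

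**3. What the same model also carries.** Under full mediation the coefficient of M averages 0.50 and 0.30, the true values of b, and rejects in 100% of runs. Without M, β6 averages about 0.25 (0.5 × 0.5 = 0.25) and 0.10 (0.3 × 0.3 = 0.09); with M it is about 0. Suppose M were also analysed as a secondary outcome, which would give a treatment-to-M test. Requiring both that test and the M coefficient to be significant rejects in 89% (0.5/0.5) and 49% (0.3/0.3) of runs, and in 5 to 6% when treatment does not move M. So the ingredients may exist, but the SAP does not combine them.

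**4. A proper two-path test still needs an assumption.** In a separate model with baseline M and baseline outcome as covariates (4000 runs), set a = 0.5 and b = 0, so there is no indirect effect. An unmeasured residual correlation between M and the outcome of 0.1, 0.2 or 0.3 makes the two-path test reject in 24%, 69% and 93% of runs. Mediator-outcome confounding therefore has to be addressed openly.

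**5. The moderation term, conditionally.** If M is its baseline value M0 and the added term is literally the two-way γ·T·M0, it contributes the same amount at every visit. The month-12 contribution minus the baseline contribution is γ·T·M0 − γ·T·M0 = 0, so the term says nothing about moderation of β6. A three-way term, M0 × Intervention × visit, does. The SAP does not say that M is baseline-only. If a three-way term was intended, it only needs writing out.

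**The case against.** The interaction clause names only the moderator. One can fairly read the sentence as giving mixed regression for both roles and spelling out the moderator step alone, leaving the mediator step unwritten. Centring the independent variables implies that M enters as a main effect, and that coefficient is the M-to-outcome path adjusted for treatment. The secondary-outcome models may supply the treatment-to-M path. References 53 and 54 may describe the rest. The analyses are also exploratory by the SAP's own account.

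All of this stands as a limit on the point. A reader might infer that the trial's mediation analysis will report effect modification under the wrong name. That follows from the literal wording, but the documents do not establish it: no sentence says that the interaction coefficient is the mediation test, and the cited references cannot be seen.

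The objection does not supply what is missing. The M coefficient is not given a mediation role, the psychosocial scales are not listed as secondary outcomes, no step combines the paths, and no indirect effect or mediator visit is stated.

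**Conclusion.** The point holds as a minor one. The only method the SAP states for mediators names a term that cannot settle mediation in either direction, and the steps that could are not linked. That conclusion is structural and rests on the SAP text alone; it would soften if references 53 and 54 set out the missing steps.

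The percentages illustrate the structure under assumed variances and path values. They should not be taken as error rates for this trial. Nor do the documents support extending the point to the main results: the co-primary tests, α and sample size do not use this analysis.

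The SAP's visits (months 6, 12, 18) and the Protocol's (5, 8, 14, 20 months) do not match. That concerns the primary analysis and should be raised separately. It matters here only because a mediator visit must be placed before a defined primary visit.

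**What to change.** Write moderation and mediation as two analyses, and state each variable's role and measurement visit.

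- **Moderation.** Use baseline M and test M × Intervention × primary visit, with all lower-order terms.
- **Mediation.** Use M measured after randomisation and before the primary visit, preferably at a visit all cohorts attend, because "Participants enrolled in the last cohorts will not have as many follow-up evaluations as those enrolled in initial cohorts". Estimate treatment to M, and M to outcome adjusting for treatment (a treatment × M term may be kept), with baseline M, gender and cohort in the models. Report the indirect effect with an interval, and state that it assumes no unmeasured mediator-outcome confounding. The interval method and any sensitivity analysis are the sponsor's choice.
- **Interpretation.** State that the interaction term is not a test of mediation. If references 53 and 54 already give these steps, write them into the SAP.

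The cost is SAP wording and modest extra analysis, with no new visits or participants. This assumes that the coping and social-support scales are in the planned questionnaires; Protocol section 2a names resilience and emotional status but not those two. The analyses stay exploratory.
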